At NU, the trial will be primarily implemented at the Robert H. Lurie Comprehensive Cancer Center. [name] is Director of the cancer center and will ensure that this trial is integrated into the cancer center clinics to facilitate recruitment. Cancer Center data indicate that ~6000 new patients/year are seen at the NU cancer center. Preliminary data ascertained for this proposal showed that, among 127 eligible cancer patients screened, 17 were smokers (13%) and 12 (71%) agreed to enroll in a smoking cessation program. Thus, based on ~6000 patients available for screening/year, we expect that ~780 will be smokers and ~546 will be interested in this study. Given the trial requirements and inclusion/exclusion criteria, we estimate that we can enroll ~10% of these patients for this trial (Martinez et al., 2009) or ~55 patients/year at NU (total sample at NU = 187 over 4 years).

Both PENN and NU will supplement recruitment with referrals from physicians and other cancer care providers at various cancer treatment centers within the Philadelphia and Chicago metropolitan areas.

Based on our extended therapy and bupropion trial with cancer patients ([name] et al., 2010a, 2010b), we expect that <20% of participants will withdraw from the trial and ~70% of participants will complete follow-up evaluations, which will exceed rates in varenicline trials (Jorenby et al., 2006). As is advised in smoking cessation trials (Hughes et al., 2003), intent-to-treat will be used for primary analyses, with missing outcome data coded as smokers (even due to death).

3. Key Inclusion Criteria

Eligible subjects will be males and females:

1. 18 years of age or older who self-report smoking at least 5 cigarettes per week, almost every week (menthol and non-menthol) on average, for the last 6 months.
2. Who have been diagnosed with a primary or secondary cancer (all sites) or have experienced a recurrence of a previously diagnosed cancer within the past 5 years. Those diagnosed >5 years ago without remission will also be eligible.
3. With a Karnofsky Score of ≥ 50 or ECOG Performance Status score of ≤ 2 within 6 months of enrollment.
4. Able to use varenicline safely, based on a medical evaluation including medical history and physical examination, and psychiatric evaluation.
5. Residing in the geographic area for at least 12 months.

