Quit Day Session (Week 1): At Week 1, participants will receive a 30-minute in-person “quit-day” session to review the initial quit attempt, identify potential reasons for relapse, and review a plan for avoiding tempting situations.

Relapse Prevention Sessions (Weeks 4, 8, 12, 14, and 18): Participants will then receive 5 additional 20-minute sessions (in-person or over the telephone) at Weeks 4, 8, 12, 14, and 18 which either reinforce success and review the quit plan or reestablish a quit date and restart the cessation process. The sessions are designed to enhance awareness of the harmful effects of smoking, assist the person in developing skills to quit and avoid relapse, and instruct the smoker on varenicline use. All sessions may be audio-taped and a random 15% of sessions are assessed for protocol adherence. The counselor is blind to randomization.

Varenicline or Placebo Treatment (Weeks 0-24).

Varenicline will be used in accordance with FDA approved labeling: Day 1-Day 3 (0.5mg once daily); Day 4-Day 7 (0.5mg twice daily); and Day 8-Day 84 (1.0mg twice daily). On Day 85, participants randomized to standard therapy will be given placebo pills (resembling the 1.0mg pills), while extended therapy participants will continue with active varenicline (1.0mg twice daily). Participants will take this medication until Day 168. Extended therapy was defined as 24 weeks to be consistent with previous trials ([name] et al., 2010b).

If a participant is not able to attend a medication pick up visit (Week 4 or Week 12), the session will be completed over the phone and, if eligible, one week of study medication will be mailed to the participant from the research pharmacy. Participants will need to schedule a brief appointment in-center to complete a blood pressure evaluation before additional study medication is dispensed (session blood pressure procedures apply). If the Week 4 or Week 12 assessments cannot be completed over the phone within the session window, participants will be invited to a brief in-center appointment for a side effects assessment and blood pressure evaluation before additional study medication is dispensed (session side effects and blood pressure procedures apply).

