Participants who discontinue the study medication for 14 or more consecutive days will require approval from the Principal Investigator and Study Physician before restarting the study medication. Participants will also be required to sign a consent addendum acknowledging that re-starting medication at full dose without a dose run-up may result in increased side effects.

Varenicline Adherence.

At each session following Pre-Quit, medication adherence is evaluated by self-report and pill count. Specific strategies to address non-adherence will be used, if necessary. The varenicline adherence approach formally assesses participant reasons for non-adherence using scenarios and uses specific strategies to enhance compliance. At Week 4 (steady-state), all participants enrolled at Penn will be asked to provide a blood sample to evaluate varenicline levels as a measure of adherence. If a participant discontinues study medication for any reason for 14 or more consecutive days prior to an adherence blood draw, the blood draw will not be performed.

Mid-treatment Assessments.

Assessments will be conducted at Weeks 0, 1, 4, 8, 12, 14, 18, 24, 26, and 52 by trained RAs. These assessments will require ~30 minutes to complete and will be conducted in-person or over the telephone prior to counseling. Assessments include measures of mediating variables (e.g., affect), side-effects (including a suicidality scale), treatment adherence (pill count and collection of blister packs), concomitant medication review, carbon monoxide assessment, QOL, smoking behavior, and changes in cue-elicited smoking urges (via computer-based concurrent choice task; in-person visits only).

Side Effect Monitoring

The research team has clinical psychologists and physicians at each site to review initial eligibility and to monitor and address side effects during the trial. To reduce risk for adverse events, we carefully assess eligibility to ensure that individuals with certain pre-existing conditions that can increase adverse event risk are excluded.

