As in our past (Patterson et al., 2009; [name] et al., 2011) and ongoing (U01 DA020830) varenicline trials, a checklist and open-ended questions assess the incidence and severity of varenicline-related side effects at all time-points following the Intake Session. These assessments monitor safety, and dose reductions or suspension of medication may be indicated based on the side effect reporting. Side effects will be a study outcome and a covariate; overall frequency, changes from pre-treatment baseline (Pre-Quit) and the presence of specific side effects will all be tracked. This measure includes potential varenicline-related psychiatric events (Kuehn, 2008) and cardiovascular side effects.

Varenicline Adherence

Medication adherence will be assessed by self-report using a time-line follow-back method and by pill count and collection of used blister packs at each visit as in past varenicline trials (e.g., Gonzales et al., 2006; Jorenby et al., 2006; Ebbert et al., 2009; Niaura et al., 2008). We will also collect blood (10mL) from 50% of participants enrolled at Penn at Week 4 to assess varenicline levels as an adherence measure and to examine the validity of self-report and pill count data. An adherence measure will represent the proportion of total dose taken (adherence = > 80% of dose taken based on self-report, pill-count, and ng/ml for plasma varenicline; Catz et al., 2011).

Integrity of the Blind

Participants may be likely to notice a change in their physiological and/or psychological state that would be best noted following the two-week washout period (Week 14), and their perception may change after they experience the second potential washout period (Week 26). This follows the questions outlined by [name] et al. (2008).

Program Satisfaction

Given the negative perception that many individuals have of Chantix, understanding patient's satisfaction with the program, and how that might change between weeks 12 (standard duration) and 24 (extended duration), will provide a basis for clinical relevance. These questions were modeled after patient satisfaction questionnaires used for a variety of smoking cessation programs.

Outcomes Variables.

Abstinence (primary)

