Aim 3: The analyses will assess changes in affect and cognitive impairment as mediators of treatment arm effects at Week 24 and 52. These measures are continuous difference scores. Our sample of 374 is well above the minimum sample of 200 recommended for models of this size (Haduk, 1987; Boosma & Gabrielli, 1985). The mediation hypothesis will examine the proportion of treatment effect explained (Lin et al., 1997; Vittinghoff et al., 2009), and test with a z-score generated using the delta method. Our sample of 374 gives us 80% power to observe small effects in a 1-sample test ($\delta=0.20$) when testing at $\alpha=0.05$. There are two proposed mediating pathways between treatment and outcome, so our type-1 error will be corrected to 0.025. Our sample of 374 gives us 80% power to detect small to medium effects ($\delta=0.22$) for changes in the proposed mediators.

[figure not shown]
Data Analysis

[name] will oversee analyses. Preliminary analyses will assess sample characteristics by treatment with chi-square or logistic regression (e.g., gender, dependence, depression, disease site). These variables will also be examined for their relationship to completion of outcome assessments. Variables related to treatment arm and completion of follow-ups will be included as covariates in analyses of study aims. Compliance measures will be evaluated across treatment arms, and controlled for in primary analyses. Although we will use an intent-to-treat analysis as the primary method for evaluating study aims, we will conduct a completers only analysis of study aims and examine study aims with participants lost to follow-up due to death excluded as done previously ([name] et al., 2003).

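### The primary analyses control for medication compliance, which is measured after randomisation and, over the full course, half of it after the arms diverge on Day 85

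*Combined protocol and SAP*

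**What the plan says.** All references are to the combined protocol and SAP.

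- Section 2, Statistical Analysis, under Data Analysis: "Compliance measures will be evaluated across treatment arms, and controlled for in primary analyses". The next sentence says "we will use an intent-to-treat analysis as the primary method for evaluating study aims".
- Section 2, Accrual: "intent-to-treat will be used for primary analyses, with missing outcome data coded as smokers (even due to death".
- Study Procedures, Varenicline Adherence: "At each session following Pre-Quit, medication adherence is evaluated by self-report and pill count". Table 2 marks pill counts at Weeks 1, 4, 8, 12, 14, 18, 24 and 26.
- Treatment Measures, Varenicline Adherence: "An adherence measure will represent the proportion of total dose taken", with the cut-off "adherence = > 80% of dose taken based on self-report, pill-count, and ng/ml for plasma varenicline".
- Varenicline or Placebo Treatment (Weeks 0-24): "On Day 85, participants randomized to standard therapy will be given placebo pills", and "Participants will take this medication until Day 168". The extended arm stays on active drug over the same days.
- Data Analysis, Aim 1: a logistic model with an arm term. Covariates are allowed but not named.

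Nothing in the document withdraws the compliance sentence, limits it to compliance before Day 85, or calls the adjusted model secondary.

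**The concern.** The primary question is whether assignment to extended treatment raises abstinence at Weeks 24 and 52. A covariate measured before randomisation leaves that question intact. A covariate that arm can influence does not: part of the effect of assignment may pass through it, and conditioning on it makes the arms unlike in whatever else drives both compliance and quitting.

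The plan itself describes two routes from arm to compliance after Day 84. The Integrity of the Blind section expects that participants may perceive a change after the switch. The Side Effects section allows doses to be reduced or suspended because of side effects. Aim 3 also needs Aim 1 to be a total effect, since it first establishes that arm affects quit rates and then splits that effect into mediated and unmediated parts.

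At stake are the bias, test level and power of both primary odds ratios. The bias can go either way. Its direction depends on which arm complies better and on whether the shared cause moves compliance and abstinence the same way. The documents settle neither.

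**Working it through.** **1. The plan's own power figure.** Inputs (Power, Aim 1): 33% vs 47% at Week 24, N = 374, two-sided 5%. I assume 187 per arm, because no allocation ratio is given. With mean proportion 0.40:

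z = [0.14 × √187 − 1.96 × √(2 × 0.40 × 0.60)] / √(0.33 × 0.67 + 0.47 × 0.53) = (1.914 − 1.358) / 0.686 = 0.81

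This gives 79% power, in agreement with the stated 80%. The unadjusted odds ratio is (0.47/0.53)/(0.33/0.67) = 1.80. The calculation contains no compliance term.

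**2. When compliance accrues.** The 24-week kit carrying the randomisation number is assigned at enrolment, so every compliance measurement is post-randomisation. Scheduled doses are:

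- Days 1-3, once daily: 3
- Days 4-7, twice daily: 8
- Days 8-84, twice daily: 77 × 2 = 154, so 165 by Day 84
- Days 85-168, twice daily: 84 × 2 = 168, so 333 in all

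The share after Day 84 is 168/333 = 50.5%. Four of the eight pill-count visits (Weeks 14, 18, 24, 26) also fall after it, and Week 26 comes after the Week 24 outcome.

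If total dose means the 24-week schedule, a patient who has taken every dose to Day 84 stands at 165/333 = 49.5%. Exceeding 80% needs at least 267 doses (0.80 × 333 = 266.4), so 102 of the remaining 168 (61%). On that reading nobody can be classed adherent before the arms diverge.

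**3. Illustration of the consequence.** All compliance inputs here are assumptions. A standard normal variable U drives both outcomes: logit P(comply) and logit P(abstinent) are each linear in U with the same slope. Intercepts are solved for the stated marginal rates. Standard-arm compliance is 60-80%. The fitted model is logistic on arm plus compliance, n = 374, with a Wald test at 1.96. Ranges cover the three standard-arm compliance rates 60, 70 and 80%.

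Type I error, with 40% abstinent in both arms:

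| Compliance gap | Slope 0.5 | Slope 1.0 | Slope 1.5 |
|---|---|---|---|
| 0 points | 5.0% | 5.0% | 5.0% |
| 10 points | 5.1% | 6.2-6.3% | 8.5-8.8% |
| 15 points | 5.3% | 7.7-7.9% | 12.6-13.8% |

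A 5-point gap gives 5.0-5.9% over these slopes. At slope 1.0, with the extended arm complying better by 15 points, the null odds ratio is 0.90. If U acts in opposite directions on compliance and abstinence, it is 1.12 (type I error 8.0-8.3%).

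Week 24 power at 33% vs 47%, extended arm complying better (unadjusted about 79%):

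| Compliance gap | Slope 0.5 | Slope 1.0 | Slope 1.5 |
|---|---|---|---|
| 5 points | 77% | 74-75% | 72-73% |
| 10 points | 75% | 68-69% | 62-63% |
| 15 points | 72-73% | 61-63% | 50-52% |

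If the extended arm complies worse by 15 points, the adjusted odds ratio is 1.87, 2.03-2.04 and 2.24-2.30 for the three slopes. With equal compliance it is 1.80, 1.82-1.83 and 1.86-1.89.

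At Week 52, power stays above 99% at the expected 28% vs 56%. At the fallback 14-point difference (28% vs 42%, unadjusted 81%), 15 points better compliance gives 74-75%, 64-66% and 55-56%.

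**4. A second model, in which compliance itself helps quitting.** Assumed: standard-arm compliance 50%, compliance log odds ratio 1.1 on quitting, and U with slope 1 on compliance and 0.5 on quitting. With the extended arm 10 points higher, Week 24 power is 63%, and the test rejects in 8% of trials when quit rates are equal. At 20 points the figures are 36% and 21%. With equal compliance they are 84% and 5%.

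**The case against.** Five points can be made for the plan.

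- **The window is not fixed.** The sentence speaks of compliance measures without naming a period. The plasma level is taken at Week 4, when both arms receive the same blinded treatment, so arm should not affect it. This stands in part: the half-after-divergence count applies to a full-course measure. But the adherence definition refers to total dose, pill counts run to Week 26, and nothing restricts the covariate to the early period.
- **Intent-to-treat concerns who is analysed.** A covariate removes and reassigns nobody. That is fair. The conflict is with the effect that an intent-to-treat analysis is meant to estimate, not with the analysis population.
- **An unadjusted sample size does not forbid an adjusted model.** Correct; the power section is only weak support.
- **Missing compliance.** The plan has no rule for it, but does not say such patients are dropped. If they were, the rule that missing outcomes count as smoking would be undercut. The number is unknown, so this remains a gap and not a demonstrated harm.
- **The gap may be small.** Matching placebo, central kits, equal counselling and adherence support in both arms all work against a difference. With equal compliance there is no inflation, and at 5 points little. The larger figures need gaps of 10-15 points and slopes of 1.0-1.5; slope 1.5 implies a compliance-abstinence odds ratio of about 3.4-3.9. All of this stands, but whether the arms complied equally is known only after the data are in, so it cannot justify the sentence in advance.

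**Conclusion.** The concern holds. Followed as written, the plan puts a post-randomisation variable that arm can affect into the models for both primary endpoints, so the arm odds ratio does not estimate the effect of assignment. That conclusion rests on the text and the dosing calendar and is firm. The size is not: it depends on assumed compliance rates, gaps and shared causes, and runs from no distortion of the test (equal compliance) to a type I error of about 13% and Week 24 power of about 50% (15-point gap, slope 1.5). The sentence should be corrected before the primary analysis, because otherwise two analysts could report different primary odds ratios from the same plan.

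**What to change.** - In Data Analysis, delete the second half of the compliance sentence, so that compliance is only compared across arms.
- There and under Aim 1, state that the primary Week 24 and Week 52 models contain arm plus named baseline covariates only, on all randomised participants, with missing outcomes counted as smoking.
- Report compliance by arm descriptively. Label any compliance-adjusted or complier analysis secondary.
- If a compliance term is kept in the primary model, limit it to compliance up to Day 84 and add a rule for missing values.
- For consistency, say in the Side Effects and the Depression and Anxiety sections that their covariate role in the primary models is confined to baseline values. Both measures are called covariates there without that limit.

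The cost is wording only. No new data are needed, and N = 374 and the power calculation stand. What is given up is a small possible precision gain: if compliance were equal, power with the term would be 79-84% over slopes 0.5-2.0, against about 79% without it.

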Table 1. Study Timeline

| Tasks/Months | 1 | 12 | 24 | 36 | 48 | 60 |
|---|-----|-------|-------|----|----|--------|
| Refine and test DMS and Train Staff (1-3) | X—X | | | | | |
| Recruitment/baselines (3-48) | X | ----- | | | X | |
| Treatment (3-54) | X | ----- | | | | X |
| Outcome assessments (15-60) | | X | ----- | | | X |
| Analysis/manuscripts (48-60) | | | | | X | -----X |

DRUGS OR DEVICES

Study Medication

Dosing

Varenicline will be used in accordance with FDA approved labeling: Day 1-Day 3 (0.5mg once daily); Day 4-Day 7 (0.5mg twice daily); and Day 8-Day 84 (1.0mg twice daily). On Day 85, participants randomized to standard therapy will be given placebo pills (resembling the 1.0mg pills), while extended therapy participants will continue with active varenicline (1.0mg twice daily). Participants will take this medication until Day 168.

Supply, Preparation, Storage, Packaging and Dispensing of Study Medication

Varenicline and matching placebo will be provided at no-cost by Pfizer and packaged and stored at the Penn Investigational Drug Service (IDS). Penn IDS will oversee the randomization and labeling of all study medication, and will assign each kit, which contains 24 weeks of medication for one subject, a unique Pharmacy Randomization Number (PRN). Once a new subject is enrolled and eligible, Penn IDS will assign the subject the next available PRN. The research staff will then label the blister packs with the subject's study ID number. The PRN and study ID number must match for each blister pack a subject receives. A centralized system will help to preserve internal validity and maintain study blinding of clinical treatment site personnel.

The study coordinator at Penn will work with Penn IDS to ensure that an adequate supply of medication is available at all treatment sites. At NU, the study investigators will store the study drug in locked cabinets. Medication supply, in increments, will be given to participants at Pre-Quit, Weeks 4 and 12.

Regular study drug reconciliation will be performed to document drug assigned, drug consumed, and drug remaining. This reconciliation will be logged on the drug reconciliation form, and signed by the research staff member who completed the reconciliation.

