We will also frequently assess participant treatment reactions with established varenicline symptom checklists and validated suicidality and depression scales. These assessments will be conducted at each visit before, during, and after the treatment phase. Also, given recent reports indicating the potential risk for adverse cardiovascular effects from varenicline (Singh et al., 2011 and www.fda.gov/Drugs/DrugSafety/ucm259161.htm), blood pressure will be assessed at each in-person visit to monitor cardiovascular reactions to study medication.

We will use an established coding and reporting system for side effects used in our ongoing multi-site varenicline trial (U01 DA020830). In this system, study personnel are trained by physicians and psychologists to administer established side effects measures, including validated scales of depression and suicidality. If a side effect report or a score on an established scale indicates a safety concern, site PIs and physicians/psychologists are immediately notified and will determine a course of action (e.g., continue to monitor, stop medication). Participants are given contact information so that, if an adverse event occurs, they can contact study physicians 24-hours a day. These side effects are also coded and managed by PIs and site physicians/psychologists. All serious adverse events are reported to the IRB, NIH, FDA, and Pfizer in accordance with data safety and monitoring reporting procedures, and they may also be referred to an out-patient department at PENN/NU or to the ER. Lastly, a study-specific Data Safety and Monitoring Board will be convened for this trial to monitor side effects.

Outcome Assessments.

The primary outcome variable is 7-day point prevalence abstinence at Weeks 24 and 52, confirmed with CO (Hughes et al., 2003). All participants will be asked to attend the center at Weeks 24 and 52 and CO will be collected for all participants to avoid potential bias. Other outcomes include: 7-day point-prevalence abstinence (CO-verified) at Week 12 and 26, smoking rate, prolonged abstinence to Weeks 12, 24, 26, and 52 (relapse defined as 7 consecutive days of self-reported smoking, after a 2-week grace period), continuous abstinence at Week 12, 24, 26, and 52 (no smoking between the quit day and the follow-up measure), time to 7-day relapse (no grace period), lapse and recovery events, and QOL.

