Aim 1: Compare standard varenicline treatment (12-weeks active then 12-weeks placebo) to extended varenicline treatment (24-weeks active) for treating nicotine dependence among cancer patients. The hypothesized effect of treatment arm (i.e., the difference in quit rates between subjects receiving standard or extended treatment) will be tested by a treatment arm term in a binomial family with logit link (logistic regression) model that possibly includes terms for covariates. Outcomes of the logistic regression analyses will be characterized by odds ratios (e.g., odds of quitting smoking) and 95% confidence intervals. Although quit-rates at the end of 24 and 52 weeks will represent our primary outcome variables, similar logistic regression analyses will be performed for other assessments of quit rates (e.g., quit rates at Weeks 12 and 26). This model will be used for measures of prolonged and continuous abstinence as well. In addition, as many participants will fail to become completely abstinent, the negative binomial family log link for count data will be used to examine the main effects of treatment arm on changes in smoking rate. Time to (recurrent) event models will be fitted using Cox regression, stratified by event sequence, as in [name] et al. (2010).

Aim 2: Assess effects of extended varenicline therapy on QOL and varenicline side effects. Repeated-measures MANOVA will examine differences across treatment arms in mental and physical QOL over the trial. Covariates will be included, such as medical treatment history. We will compare treatment arms in terms of the frequency of severe side effects (individual and total). Logistic regression will test against the lower boundary on percent reporting only mild-moderate (i.e., < severe) side effects. The hypothesis test for equivalence is whether the OR is out of the prescribed range for the difference between the treatment arms.

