Participants will also be told that varenicline may impair their ability to perform tasks requiring judgment or motor and cognitive skills and that they should proceed with caution in this regard until they are certain that varenicline does not affect their performance. Participants will be told that varenicline may be associated with somnambulism (sleep walking) that may result in harmful behavior to self, others, or property, and if they notice such behaviors that they should discontinue varenicline and notify the study staff after seeing their medical provider. Participants will also be advised that Chantix may affect their response to alcohol including lower alcohol tolerance, aggressive behavior, or impaired memory following consumption of alcohol. Participants will be instructed to minimize alcohol intake (no more than 3 drinks per occasion or within a 24-hour time period) while taking varenicline. Participants will be advised to inform the study staff if they are taking or plan to take any prescription or over-the-counter drugs. Women will be advised to notify the study staff if they become or intend to become pregnant during the study period. The research team has extensive prior experience conducting smoking cessation trials with varenicline.

Withdrawal. Many individuals who quit tobacco use exhibit a pattern of symptoms associated with withdrawal from tobacco use. These symptoms can include: sadness and anxiety, irritability, difficulty concentrating, anger, appetite change and weight gain, insomnia, and decreased heart rate. Eliminating the risk for these would not be possible, although in most cases these events are short-lived and have low intensity, lasting for 1-2 weeks. Use of varenicline (by all participants for the first 12 weeks of the study) will also minimize the severity of withdrawal symptoms and behavioral counseling will also offer strategies for reducing withdrawal. The study personnel will be trained to recognize these symptoms and educate the participants about them (e.g., their duration, methods for reducing them).

Blood Draws. Blood draws may result in bruising and/or slight bleeding at the needle site. This is rare and happens infrequently. Occasionally, blood drawing results in a feeling of faintness. This too is rare. A trained professional will draw blood, so the chances of these discomforts are minimal. Procedures are in place to ensure that PHI is not linked with the results of this research.

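### The primary abstinence models prespecify no adjustment for smoking status at the end of the 12 weeks of identical treatment, a valid covariate already collected that would add power at Week 24

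*Combined protocol and SAP*

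**What the plan says.** **Common period.** Under Study Medication, Dosing, all participants follow one active schedule to Day 84. Then: "On Day 85, participants randomized to standard therapy will be given placebo pills", while the extended arm stays on active drug, and "Participants will take this medication until Day 168". Potential Study Risks, Withdrawal, confirms this: "Use of varenicline (by all participants for the first 12 weeks of the study". The supply section adds: "Medication supply, in increments, will be given to participants at Pre-Quit, Weeks 4 and 12".

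**Primary model.** Data Analysis, Aim 1, says that the arm effect "will be tested by a treatment arm term in a binomial family with logit link (logistic regression) model that possibly includes terms for covariates". No covariate is named. The opening paragraph of Data Analysis selects covariates by their relation to treatment arm and to completion of follow-up.

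**Week 12 data.** These are treated as a further outcome. Outcome Assessments lists "7-day point-prevalence abstinence (CO-verified) at Week 12 and 26", and Aim 1 adds that "similar logistic regression analyses will be performed for other assessments of quit rates (e.g., quit rates at Weeks 12 and 26"). No stated analysis uses them as a covariate or starting point.

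**Time-to-event models.** "Time to (recurrent) event models will be fitted using Cox regression, stratified by event sequence", with reference to a cited earlier trial. No time origin is given.

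**The concern.** The blinded treatments are the same until Day 85, so randomised arm cannot influence whether a participant is smoking on Days 78–84. Adjusting for that status carries none of the usual danger of conditioning on a post-randomisation variable. It is probably among the strongest available predictors of Week 24 abstinence, and the data exist: daily smoking is recorded by timeline follow-back at every visit after Intake.

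The word *possibly* allows the adjustment but does not prespecify it. A rule based on arm and follow-up completion would bring it in only by accident. The planned control for compliance is no substitute, because adherence is defined as the share of the total dose, which includes dosing after the arms diverge. At stake is power in a Week 24 comparison sized with no reserve.

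**Working it through.** **Inputs.** From Power, Aim 1: 33% v 47% at Week 24, 374 participants, alpha 0.05; the Power section makes all tests two-sided. Missing outcomes count as smoking (Accrual), so the sample is not reduced. Equal allocation, 187 per arm, is assumed. The documents give neither Day-84 abstinence for this trial nor its link to Week 24. I take 20–60% abstinent and a within-arm odds ratio (OR) of 2 to 20. The nearest figure is a 34% end-of-treatment quit rate from a small varenicline study cited in the Background.

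**Step 1: the plan's figure.** z = [0.14 − 1.96 √(2 × 0.40 × 0.60 / 187)] / √[(0.33 × 0.67 + 0.47 × 0.53) / 187] = (0.14 − 0.0993) / 0.0501 = 0.81, so power is 79.2%. The stated 80% is reproduced.

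**Step 2: the same test as an unadjusted logistic arm term.** Write w = n p(1 − p) for each arm; the information is w₀w₁/(w₀ + w₁). Here w₀ = 41.35, w₁ = 46.58 and the information is 21.90, so SE = 0.2137. The OR is 1.80 (log 0.588), z = 2.75, and power is Φ(2.75 − 1.96) = 78.6%.

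**Step 3: add Day-84 status (worked cell: 40% abstinent, OR 10).** The overall rates stay at 33% and 47%.

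- Day-84 smokers, 112.2 per arm: 13.9% v 26.3%, w = 13.4 and 21.7, information 8.29.
- Day-84 abstainers, 74.8 per arm: 61.7% v 78.1%, w = 17.7 and 12.8, information 7.42.
- Check: 0.6 × 13.9 + 0.4 × 61.7 = 33.0; 0.6 × 26.3 + 0.4 × 78.1 = 47.0.
- Total information 15.72, SE 0.252. The conditional OR is 2.21 (log 0.794), z = 3.15, and power is Φ(1.19) = 88.3%.

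**Step 4: other cells.** Unadjusted power is 78.6% by formula and 78–80% by simulation.

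| Assumed OR | Formula, 20–60% abstinent | Simulation, 34–50% (3,000 trials per cell) | Taken together, about |
|---|---|---|---|
| 2 | 79.3–79.6% | not run | gain of 1 point or less |
| 3 | 80.4–81.2% | 81.3–82.2% | 80–82% |
| 5 | 82.2–83.9% | 84.1–84.7% | 83–86% |
| 10 | 85.1–88.3% | 88.8–90.3% | 85–89% |
| 20 | 87.9–92.6% | 93.8–94.3% | 89–94% |

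The last column also draws on simulation over 20–60%. The methods differ by one or two points. Size under the null was 4.4–5.2%.

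**Step 5: risk difference.** Unadjusted SE: √(0.4702 / 187) = 5.0 points. In the worked cell the average within-status variance, summed over arms, is 0.6 × (0.139 × 0.861 + 0.263 × 0.737) + 0.4 × (0.617 × 0.383 + 0.781 × 0.219) = 0.351, so SE = √(0.351 / 187) = 4.3 points. The difference itself stays at 14 points.

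**Step 6: what reduces the gain.**

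- *Where the effect falls (40–50% abstinent).* If all 14 points arise in Day-84 smokers, power is 80–81% (OR 5) or 83–84% (OR 10). If all arise in abstainers, it is 88–91% or 94–97%.
- *Missing diaries.* If 20% of Day-84 abstainers have no diary and are coded as smoking, power is 81%, 83%, 86% and 89–91% at OR 3, 5, 10 and 20.
- *Week 52.* At the expected 28% v 56%, unadjusted power already exceeds 99.9%. At the fallback 14-point difference (28% v 42%) it is 81.3%. Any gain there depends on how well Day-84 status predicts smoking 40 weeks later.

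**The case against.** The strongest reply is that nothing here is an error. The unadjusted intention-to-treat test is valid, the sizing is correct, and the plan's wording leaves room for covariates. The gain rests on an OR found nowhere in the documents. The Background also argues that longer treatment helps people who have lapsed to recover, which points towards the less favourable case in Step 6. All of this stands, and it makes the point an improvement, not a correction.

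A reader might infer more than the documents support:

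- *That chance imbalance at Day 84 biases the result.* It does not. One standard error of imbalance (about 5 points) would shift the Week 24 difference by 1.3–3.1 points, but that variation is already inside the 5.0-point SE. It is the same efficiency gain seen from another side.
- *That the unstated Cox origin makes the hazard ratio (HR) arbitrary, say 0.60 or anything from 0.71 to 0.95.* That span mixes different truths. With an assumed HR of 0.60 after Day 85 that lasts to Week 52, the quit-day HR is 0.71–0.87, depending on the assumed share of early relapse. Values of 0.88–0.95 need an effect that ends at Day 168, and then the HR from Day 85 to Week 52 is itself 0.83–0.85. Quit day is the natural reading of the abstinence definitions, and the cited trial may state it. Starting at Day 85 is a trade-off, since a first-relapse model then drops earlier relapsers.
- *That Week 12 mediator scores must be used in Aim 3.* The gain rests on assumed correlations and is not shown for the mediation test itself.
- *That testing Week 12 abstinence by arm does harm.* It is listed among other outcomes; apart from visits late in the window, a difference there is chance. This is a matter of labelling.

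**Conclusion.** The point holds as a cheap gain in efficiency and prespecification. Day-84 smoking status is a legitimate covariate, it is already collected, and no stated analysis uses it. Under ORs of 3 to 20 and 20–60% abstinent at Day 84, Week 24 power rises from about 79% to between 80% and 94%. The upper end needs a very strong link and a middling abstinence rate. The gain is negligible at OR 2, smaller if the benefit falls mainly on Day-84 smokers, and nil at the expected Week 52 rates. It does not show that the primary analysis is invalid or that the trial was missized.

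Three minor points go with it. A single Cox arm term from quit day would average in weeks in which the HR is 1 by design. Data Analysis, Aim 3, places the switch to placebo at Week 14, while the dosing sections place it at Day 85. The cue-elicited urge task is a named mediator, but Table 2 gives it no Week 14 value and no other analysis time point is named.

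**What to change.** **Main change.** In the Week 24, 26 and 52 abstinence models:

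- Prespecify one covariate: 7-day smoking status on Days 78–84 from the timeline follow-back. If the Week 12 visit fell earlier, use the last 7 days before it. Fixing the days matters because that visit may fall up to a week late, after the arms diverge.
- Code a missing diary as smoking, so that all randomised participants stay in the model.
- Report the standardised risk difference beside the conditional OR, with the unadjusted result as a sensitivity analysis.
- Present Week 12 abstinence by arm as a check of balance.

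**Minor changes.** State the Cox time origin and the form of the arm effect, and consider a supplementary HR from Day 85. Reconcile the Week 14 and Day 85 wording. Name an analysis time point for the urge task. Adjusting Week 14 mediators for their Week 12 scores is optional.

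**Cost.** SAP wording before unblinding and a little more analysis; no new data. The one real drawback is that the conditional OR (about 1.8–2.6 in these scenarios) cannot be compared with the 1.81 used for sizing, which is why the risk difference is needed beside it.
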